9.2 CLINICAL LABORATORY PARAMETERS

Laboratory assessments include hematology, clinical chemistry, and urinalysis:

- Clinical Chemistry: Total Bilirubin, Aspartate Aminotransferase (AST), Alanine Aminotransferase (ALT), Blood Urea Nitrogen (BUN), Glucose, Potassium, Sodium, Calcium, Alkaline Phosphatase, Chloride, Creatinine, Carbon Dioxide (CO2).
- Hematology: Hemoglobin, Hematocrit, Erythrocytes, Leukocytes + differential, Thrombocytes (platelet count).
- Urinalysis: pH, Color, Transparency, Specific Gravity, Urobilinogen, Ketones, Protein, Glucose

All laboratory parameters will be presented in Système International (SI) units.

Quantitative results (including actual values and change from baseline) will be summarized using descriptive statistics by baseline and post-baseline visit for each laboratory test group above. Laboratory test results will be assigned an LH classification according to whether the value was below (L) or above (H) the normal reference range (some urinalysis labs are assigned only normal and abnormal classifications) (See also Appendix 14.2). Values outside the normal range will also be classified as to whether

they were potentially clinically significant (Appendix 14.3). Shift tables cross-tabulating the baseline and post-baseline classifications (below (L), Normal (N), or above (H) the reference range), by visit, will be provided.

All laboratory data will be included in the listings. A pregnancy listing will be provided separately.

9.3 OTHER SAFETY ENDPOINTS

9.3.1 Vital Signs

Vital signs include weight (kg), height (cm), temperature (°C), systolic and diastolic blood pressure (mmHg), respiration rate (breaths per minute), and pulse rate (bpm).

Quantitative results (including actual value and change from baseline to each post-baseline visit) will be summarized using descriptive statistics by baseline and post-baseline visit for each parameter.

Listings of vital signs will be provided.

9.3.2 Electrocardiogram (ECG)

The 12-lead ECG parameters including value and change from baseline will be summarized using descriptive statistics by baseline and post-baseline visit. Overall ECG results are interpreted as normal, abnormal (not clinically significant) or abnormal (clinically significant). The number and percentage of subjects in each category will be summarized by baseline and post-baseline visit.

A subject listing will be provided.

9.3.3 Physical, Neurological, and Developmental Examinations

Physical examination results were interpreted as normal, abnormal (not clinically significant) or abnormal (clinically significant). Neurological examination results were interpreted as normal or abnormal. Physical, neurological, and developmental examination findings will be summarized and listed.

9.3.4 Neurosteroid Levels

The baseline and post-baseline values and the arithmetic changes from baseline of the neurosteroid levels will be summarized using descriptive statistics and listed.

To examine response by neurosteroid levels, change from baseline in 28-day seizure frequency will be summarized in the subsets of the ITT subject population with low allopregnanolone-sulfate (Allo-S) levels, defined as baseline Allo-S \leq 2,500 pg/mL, mid Allo-S levels, defined as baseline Allo-S $>$ 2,500 pg/mL and $<$ 6,000 pg/mL, and high All-S levels, defined as Allo-S \geq 6,000 pg/mL.

9.3.5 Tanner Staging

The Tanner scale (also known as the Tanner stages) is a scale of physical development in children, adolescents, and adults. The scale defines physical measurements of

development based on external primary and secondary sex characteristics. Subjects will be evaluated and rated as Tanner I, Tanner II, Tanner III, Tanner IV and Tanner V. Tanner staging will occur at Screening (Visit 1), Visit 8 (Week 52) and will continue to be assessed annually for the duration of the subject's participation in the open-label phase and at the final OL visit.

The number and percentage of subjects of each category will be summarized by Screening and OL visit, and a listing will be provided.

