4.5. Discontinuation of Subjects

A subject may withdraw — or their parent/LAR may withdraw the subject — from the study at any time for any reason without prejudice to their future medical care by the physician or at the hospital. The PI or sponsor may withdraw the subject at any time (eg, in the interest of subject safety). The PI is encouraged to discuss withdrawal of a subject from IP with the medical monitor when possible.

Subjects who discontinue IP treatment before the completion of the DB phase will continue to be followed per protocol and, at a minimum, subjects will be encouraged to maintain daily seizure eDiary entries until the DB phase is completed. These subjects should also return to the site after the taper for safety follow-up post taper assessments (Section 7.2.7).

If the IP is discontinued at any time, subjects should follow the 2-week taper schedule, unless otherwise medically indicated (Section 7.2.6). If the subject discontinues during the OL phase, evaluations listed for the Taper Visit are to be performed as completely as possible. Whenever possible, all subjects who discontinue should also undergo the protocol-specified Safety Follow-up Post-Taper visit (Section 7.2.7). Comments (spontaneous or elicited) or complaints made by the subject must be recorded in the source documents. The reason for termination, date of stopping IP, and total amount of IP taken must be recorded in the electronic case report form (eCRF) and source documents. Discontinuation of IP due to AEs must also be reflected on the AE eCRF page.

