7.2.5.3. Visit X - Additional Maintenance Visits in the Open-Label Period Phase

If the subject continues in the OL phase beyond Week 68, the subject must return for a clinic visit every 16 weeks (\pm 14 days) to complete the following study procedures/assessments:

- Vital signs (All Visits: to include BP, HR, RR, body temperature, and weight; only height will be measured annually)
- Physical, neurological, and developmental examination
- Clinical laboratory tests (to include CBC with automated differential, creatinine, blood urea nitrogen, and comprehensive metabolic panel)
- Urinalysis (annually)
- Serum pregnancy test for females of childbearing potential
- Tanner staging (annually)
- ECG (annually)
- Investigational Product PK
- Concomitant AED review and levels if per SOC
- Neurosteroid level sample draw (annually)
- Adverse events
- Seizure and medication diary review
- CSHQ
- BRIEF
- ABC-C
- PedsQL-FIM
- QI-Disability
- CGI-C (parent/caregiver/LAR identified behavioral target)
- CGI-I (parent/caregiver/LAR and clinician)
- Dispense IP

If the subject continues in the OL phase beyond Week 68, a telephone follow-up visit will occur in between clinic visits (8 weeks \pm 7 days after each clinic visit) to assess the following:

- Adverse events
- Seizure and medication diary review

7.2.6. Final Open-Label Period Visit or Taper Visit (or at time of Early Termination \pm 14 days)

The following study procedures/assessments to be completed during the final OL visit or taper visit at the time of early termination:

- Vital signs (to include BP, HR, RR, body temperature, weight, and height)
- Physical, neurological, and developmental examination
- ECG
- Clinical laboratory tests (to include CBC with automated differential, creatinine, blood urea nitrogen, and comprehensive metabolic panel)

- Urinalysis
- Serum pregnancy test for females of childbearing potential
- Tanner staging
- Investigational Product PK
- Concomitant AED review and levels if SOC
- Neurosteroid level sample draw
- Adverse events
- Seizure and medication diary review
- CSHQ
- BRIEF
- ABC-C
- EEG
- PedsQL-FIM
- QI-Disability
- CGI-C (parent/caregiver/LAR identified behavioral target)
- CGI-I (parent/caregiver/LAR and clinician)
- Dispense IP

7.2.7. Safety Follow-up Post Taper (2 Weeks Post Last Dose/Investigational Product Taper \pm 3 days)

The following study procedures/assessments to be completed during the safety follow-up post-taper visit:

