7.6.2. Vital Signs

Vital signs including HR (bpm), RR (breaths/minute), body temperature (C/F), BP (mmHg), and weight will be collected at every clinic visit starting with Visit 1 other than the Safety Follow-Up Visit. Height will be collected at Visit 1 (screening) (during DB phase) and during the OL phase at Visit 7 (Week 36), at Visit 8 (Week 52), annually thereafter (except for the Safety Follow-up Visit), and at the Final OL Visit.

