9.14. Safety Analyses

All safety analyses will be performed in the Safety Population. The results in the DB and OL phases will be summarized separately. In both phases, the results will be summarized by the DB treatment actually received and, for the OL phase of the study, combined over the treatment groups. The number and percentage of days that subjects received investigational product, the highest percentage of the maximum allowable daily dose (1800 mg or 63 mg/kg) that subjects received, and the total amount of investigational product received will be summarized. For the open-label phase, they will be summarized over just the open-label phase as well as over the entire study (combined DB and OL phases) but the classification by the double-blind treatment applies only for the open-label phase summary. The summarization over the entire study will include the double-blind data only from subjects who were in the GNX group during the double-blind phase, regardless of whether they entered the open-label phase, and all the subjects from the open-label phase.

Adverse events will be tabulated by overall, system organ class, and Preferred Term using the Medical Dictionary for Regulatory Activities (MedDRA) coding system. Incidence and percentage of AEs will be presented. Additional tables, with AEs classified by severity and by only those related to drug as assessed by the PI will be presented. Subset listings will be produced for AEs that cause withdrawal and for SAEs. Clinical laboratory tests (hematology, chemistry and urinalysis), vital signs and ECGs will be summarized using descriptive statistics including changes from baseline. In addition, shift tables cross-tabulating the baseline and post-baseline low/normal/high classifications by visit will be provided for the laboratory tests. Physical, neurological and developmental examinations will be summarized using number and percentage of subjects with abnormalities.

The Tanner scale (also known as the Tanner stages) is a scale of physical development in children, adolescents and adults. The scale defines physical measurements of development based on external primary and secondary sex characteristics. Subjects will be evaluated and rated as Tanner I, Tanner II, Tanner III, Tanner IV and Tanner V. The Tanner scale is administered following the first dose, only during the OL phase of the study.

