1.1.2 Secondary Objectives

- To assess the effect of GNX on primary seizure rate in biomarker-positive subjects.
- To assess behavioral/neuropsychiatric changes in subjects receiving GNX compared with subjects receiving PBO as adjunctive during the 17-week double-blind (DB) phase.
- To assess the safety and tolerability of GNX compared with PBO as adjunctive therapy during the 17-week DB phase.
- To assess pharmacokinetic (PK) parameters in subjects receiving GNX doses up

to 63 mg/kg/day (1800 mg/day maximum) throughout the study.

- To assess the long-term efficacy of GNX when administered as adjunctive therapy throughout the open-label (OL) phase.
- To assess the long-term safety and tolerability of GNX when administered as adjunctive therapy throughout the OL phase.

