6. For tables that summarize categorical (discrete) data, all categories between the maximum and minimum category should be presented in the table, even if there is a zero count for a particular category. A Missing category should be added to any variables to indicate missing information, if appropriate, but the percentages should be based on the number of subjects with non-missing categories.
7. If the categories are not ordered (*e.g.*, Medical History, Reasons for Discontinuation from the Study, etc.), then only those categories for which there is at least 1 patient represented in 1 or more groups should be included.
8. All fractional numeric values should be printed with a zero to the left of the decimal point (*e.g.*, 0.12, 0.3).

9. Missing descriptive statistics or p-values due to non-estimability in tables, as well as missing data in patient listings should be represented as either a hyphen (“-”) with a corresponding footnote (“ - = unknown or not evaluated”), or as “N/A” with the footnote “N/A = not applicable” whichever is appropriate.
10. Date values in the listings should be in the format ddMMMyyyy. If part of the date is unknown then leave it out; e.g., APR2019. (In the unlikely event that the date and year are available but the month is not, insert a hyphen between the date and year.)
11. Any data listing for which there were no events should be produced, stating, “There were no events.”

In addition, Section 2.1.1 contains information on reporting precision.

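### Open-label height is tabulated with no age reference and Tanner stage with no within-girl change, in girls aged 1 to 17 with no post-dose control: a modest, cheaply mended gap in descriptive safety

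*SAP*

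**What the plan says.** **Height.** SAP 9.3.1 counts height among the vital signs and treats them all alike: "Quantitative results (including actual value and change from baseline to each post-baseline visit) will be summarized using descriptive statistics". Neither document plans a z-score, percentile, growth velocity or grouping by age. On timing, Protocol 7.6.2 says: "Height will be collected at Visit 1 (screening) (during DB phase) and during the OL phase at Visit 7 (Week 36"; then come Week 52, yearly visits and the final open-label visit.

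**Tanner stage.** SAP 9.3.5 plans one table: "The number and percentage of subjects of each category will be summarized by Screening and OL visit, and a listing will be provided". There is no shift table and no link to age. Protocol 9.14 adds: "The Tanner scale is administered following the first dose, only during the OL phase of the study". The scheduled points are Screening, Week 52, yearly afterwards, and the final open-label visit.

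**Setting.** About 25 girls aged 1 to 17 are expected to be randomised. All who continue take ganaxolone in the open-label phase, and safety is shown by former double-blind arm and combined (SAP 2.1 and 9). One secondary objective is: "To assess the long-term safety and tolerability of GNX when administered as adjunctive therapy throughout the OL phase" (SAP 1.1.2).

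**The concern.** A girl of 2 and a girl of 16 differ greatly in the growth and pubertal change expected over a year. A raw mean height change in such a group reflects its age mix as much as any drug effect. No placebo data after dosing can serve as the yardstick, because the double-blind visits after Screening include neither height nor Tanner staging. Only an age reference could play that role, and the height tables have none.

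For Tanner stage, percentages per visit do not pair a girl with her own Screening stage and do not show her age.

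The SAP already uses the missing tools elsewhere. Laboratory tests get baseline-to-visit shift tables (SAP 9.2). Age-specific ranges apply to laboratory tests, PR and QRS, heart rate, blood pressure and respiratory rate (SAP 14.2.2, 14.3.2 and 14.3.3), but not to height. At stake is whether readers of the report can interpret two long-term safety summaries that the trial has already paid to collect.

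**Working it through.** The plan attaches no power, sample size or threshold to height or Tanner stage, so there is no figure to reproduce. Both illustrations below rest on assumed inputs.

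**1. Is there any control?** Screening gives the only height and Tanner stage in the double-blind phase. The next scheduled height is at Week 36 and the next Tanner stage at Week 52, or at an earlier final open-label visit. All of these fall in the open-label phase, so neither measure has placebo data after dosing. Exposure also differs within a row: at Week 52 a girl first given ganaxolone has had about 52 weeks of drug, and one first given placebo about 52 − 17 = 35.

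**2. Height: can a mean raw change show slowed growth?** Assume 25 girls followed for a year, ages uniform from 1 up to the 18th birthday, expected velocity v(a) = 11 − 10(a − 1)/16 cm/year, and within-age SD 0.8 cm/year.

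- Mean gain: mean age is 9.5, so 11 − 10 × 8.5/16 = 5.69 cm.
- SD of age: 17/√12 = 4.91. SD of velocity from age: 4.91 × 10/16 = 3.07. Total SD: √(3.07² + 0.8²) = 3.17.
- 95% range of the mean: 5.69 ± 1.96 × 3.17/√25 = 4.45 to 6.93 cm (simulation: 4.44 to 6.93).
- Uniform 20% slowing: 0.8 × 5.69 = 4.55 cm. This is inside the range, though near its lower edge; 3.7% of normally growing cohorts fall below it.

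Other assumptions, by simulation:

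| Assumed growth | n | Mean (cm) | 95% range (cm) | 20% slowed (cm) |
|---|---|---|---|---|
| 11 falling to 1 cm/year | 15 | 5.7 | 4.1 to 7.3 | 4.6, inside |
| 9 at age 1, 6 at ages 3 to 12, 0 from 16 | 25 | 4.8 | 3.7 to 5.7 | 3.8, inside |
| Same curve | 15 | 4.8 | 3.4 to 6.0 | 3.8, inside |
| Flat 5 cm/year (unrealistic) | 25 | 5.0 | 4.7 to 5.3 | 4.0, outside |

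Even in the last row the planned table carries no expected value to compare with.

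What an age reference would add: if it matched the first curve exactly, only the within-age SD would remain. The mean departure from expectation would then vary by ± 1.96 × 0.8/√25 = ± 0.31 cm, against a shortfall of 5.69 − 4.55 = 1.14 cm. A real reference will fit less well, so this is the best case.

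**3. Tanner: what do the percentages leave open?** Assume 25 girls, all assessed, none regressing, with stages I to V at 14/3/3/2/3 at Screening and 11/4/3/3/4 at Week 52.

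- Cumulative counts to stages I, II, III and IV are 14, 17, 20, 22 at Screening and 11, 15, 18, 21 at Week 52.
- Boundary crossings are therefore 3, 2, 2 and 1, or 8 stage steps in all. The table fixes these.
- It does not fix who took them. Enumeration finds 25 cross-tables with these same percentages. Between 3 and 8 girls advance, 0 to 3 move two or more stages, and the largest single move is anywhere from 1 to 4 stages.

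Age at each stage is absent in every case.

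**The case against.** The strongest reply is that, with at most about 25 girls, the listings already do this work. SAP 12.1 sorts them by subject, parameter and visit date where appropriate. Age, vital signs, Tanner stage and drug dispensation are all listed, so each girl's course can be followed and her age and approximate exposure worked out. Other safeguards sit beside the tables. Reproductive and breast events are adverse events of special interest (Protocol 8.3.1) and are tabulated (SAP 9.1). Examinations cover the genitourinary and endocrine systems (Protocol 7.6.3). A data monitoring committee reviews emerging safety data (SAP 10). All of this stands, and it bears mainly on puberty.

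It can also be said that a Tanner shift table carries no age, so a move from stage I to II looks the same at 7 and at 11. That stands too. The shift shows within-girl change but cannot by itself identify early puberty, and this is why age must appear in the listing.

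Two stronger readings are tempting, and the documents do not support them. One is that slowed growth or early puberty would go unseen in this trial; the safeguards above rule that out as a general claim. The other is that girls who leave early are lost to these summaries. Protocol 7.2.6 lists height and Tanner staging among the procedures "to be completed during the final OL visit or taper visit at the time of early termination", and Protocol 4.5 says: "If the subject discontinues during the OL phase, evaluations listed for the Taper Visit are to be performed as completely as possible". SAP 12.1 also provides that "A Missing category should be added to any variables to indicate missing information, if appropriate".

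What the reply does not meet is the height table. A listing allows case review, but it gives no summary against expected growth, and none of the other safeguards supplies one.

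**Conclusion.** The point holds for the summary tables, not for the data collected. The planned height tables cannot show departure from age-expected growth, because they have no age reference and no post-dose control. The Tanner table shows neither within-girl change nor age at stage, and that gap is partly covered by other planned outputs.

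That conclusion follows from the table layout and needs no assumption. Its size does: the growth curves, the 0.8 cm/year SD, the Tanner counts and full follow-up of 25 girls are illustrative, and the number entering the open-label phase is not given. A reader might infer that efficacy or the trial's safety conclusions are compromised. The documents do not support that: these are descriptive outputs, and no efficacy analysis uses them. This is an optional improvement, with the height z-score its most useful part.

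**What to change.** - **SAP 9.3.1:** add age- and sex-specific height z-scores from a named growth reference. Summarise the z-score and its change from baseline at each open-label visit where height is measured.
- **SAP 9.3.5:** keep the planned table. Add a shift from Screening stage to each annual visit and to the last available visit (final or early termination), with a Missing column.
- **Tanner listing:** show age at visit and time on ganaxolone, since the timing of puberty has to be judged against age.

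The cost is SAP wording and standard derivations from age, sex, height and stage already collected. SAP 11 allows such changes by amendment or in the study report. There are three downsides. A growth reference must be chosen, and it may fit some countries less well. It can show departure from expected growth but cannot separate drug from disease or co-medication. The shift table will be sparse, so the listing remains important.

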10 INTERIM ANALYSES AND DATA MONITORING COMMITTEE (DMC)

No formal interim analysis is planned for this study. After all active subjects complete the 17-week DB phase, the DB data in the database will be locked and used to perform endpoint analysis. Data collected during the open label phase will be analyzed separately.

The emerging study data will be reviewed on a regular basis by an independent DMC. The mission of the DMC will be to safeguard the interests of study participants and to enhance the integrity and credibility of the trial. To enable the DMC to achieve their mission, the DMC will have ongoing access to efficacy and safety data and data regarding quality of trial conduct and will ensure the confidentiality of these data will be preserved. A DMC Charter will provide the principles and guidelines for the DMC process. Specific details of the monitoring guidelines are provided in the DMC Charter.

11 SUMMARY OF MAJOR CHANGES IN THE PLANNED ANALYSES

There are no major changes in the planned analyses. The contents of this SAP are consistent with the most current version of the protocol.

Any future changes to these analyses will be documented in an SAP amendment or described in the clinical study report (CSR).

12 PROGRAMMING SPECIFICATIONS

12.1 FORMAT OF APPENDIX TABLES/FIGURES/LISTINGS

- Unless otherwise specified, all computer-generated tables, figures and listings (TFL) will be produced (via SAS® ODS) into RTF output, which can be imported in table format via Microsoft® Word. The TFLs should be in landscape mode with required margins: at least 1.5 inches on top (the binding margin or left for portrait output) and 1 inch on left, right, and bottom. All output should have the following headers on each page:

- Two-line header at the upper left margin:

Marinus Pharmaceuticals, Inc.
Protocol 1042-PCDH19-3002

- Header with page number and date/time at the upper right margin:

Page X of N
ddMMyyyy: hh:mm

TFLs should be internally paginated in relation to total length (i.e., page number should appear sequentially as page X of N, where N is the total number of pages within a table or listing).

2. Each TFL should be identified by in a sequential numeric order, and the TFL number should be centered above the title. The title is centered in initial capital characters and should include the population type analyzed (*e.g.* Safety Population). The title and designation are single-spaced, but are separated from the TFL by at least a double space.

Table xx.x.x.x
First Line of Title
Second Line of Title (if needed)
Population Type Analyzed

3. Column headings for tables and listings should be in initial upper-case characters.
4. Footnotes should be single spaced but separated by at least a double space from the bottom line of the TFL. The notes are left justified, with each note starting on a new line. Following the last footnote insert a single space. Tables and listings should then display the source listing number and all outputs should display the source SAS program name. For example, the set of footnotes for a table:

Note: [1] Footnote 1
[2]Footnote 2

Data Sets: xxxx, xxxx

Program Name: xxxx.sas

5. All data listings should be sorted by, treatment group and biomarker stratum with a page break between them, subject number, parameter (where appropriate), and study visit date/time where appropriate. If data for a subject and/or parameter is displayed on multiple lines, then display the subject number and/or parameter on only the first line. However, if the data for a subject or parameter is split between pages, then the subject number and parameter should be displayed on the page following the split.
6. For tables that summarize categorical (discrete) data, all categories between the maximum and minimum category should be presented in the table, even if there is a zero count for a particular category. A Missing category should be added to any variables to indicate missing information, if appropriate, but the percentages should be based on the number of subjects with non-missing categories.
7. If the categories are not ordered (*e.g.*, Medical History, Reasons for Discontinuation from the Study, etc.), then only those categories for which there is at least 1 patient represented in 1 or more groups should be included.
8. All fractional numeric values should be printed with a zero to the left of the decimal point (*e.g.*, 0.12, 0.3).

9. Missing descriptive statistics or p-values due to non-estimability in tables, as well as missing data in patient listings should be represented as either a hyphen (“-”) with a corresponding footnote (“ - = unknown or not evaluated”), or as “N/A” with the footnote “N/A = not applicable” whichever is appropriate.
10. Date values in the listings should be in the format ddMMMyyyy. If part of the date is unknown then leave it out; e.g., APR2019. (In the unlikely event that the date and year are available but the month is not, insert a hyphen between the date and year.)
11. Any data listing for which there were no events should be produced, stating, “There were no events.”

In addition, Section 2.1.1 contains information on reporting precision.

